IT Baclofen Drug Distribution Pilot Study: Proposal to Medtronic

Goal:

While ITB therapy is commonly recommended for treatment of severe spasticity due to a variety of diseases, the location of optimal drug (baclofen) delivery has not been defined in a controlled study. Furthermore, the cost of pharmacological management in these patients is significant, and optimal location for drug delivery through an implantable drug pump may have significant impact on the cost burden of maintenance refills. It is the goal of this pilot study to determine whether there is a significant therapeutic advantage to place the ITB catheter within the cervical, thoracic or lumbar region of the spine. It is also a goal of this pilot study to determine whether the origin of spasticity influences the effect of Lioresal Intrathecal (baclofen injection) on ITB catheters located in the cervical, thoracic or lumbar regions of the spine. We propose to study the impact of catheter location on the reduction in spasticity within a group of patients who are scheduled for ITB trial. Furthermore, we intend to enroll patients whose spasticity originates from two different mechanisms (SCI causing spastic paraplegia vs. cerebral palsy causing spastic spasticity of spinal and cerebral origin). In studying the impact of catheter location among patients with spinal versus cerebral origin of spasticity, the disease origin may also have a significant impact on baclofen dosing relative to the placement of the catheter.

In addition, the pharmacokinetic half-life and the variability of intrathecal baclofen is poorly understood as data is limited. In order to provide initial data regarding CSF baclofen washout, samples of spinal fluid obtained just prior to- and following IT baclofen administration will be obtained for delayed analysis. The results of these pharmacological analysis may refine the understanding of how quickly baclofen is distributed from a given catheter location, and whether it is affected by catheter location or disease origin. Since multiple catheter locations will be studied within a given patient, it also affords the opportunity to sample small amounts of CSF at key anatomical sites along the spinal axis as an independent secondary study protocol.

Hypotheses:

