Subjects who have spasticity and have consented for a trial of ITB therapy as part of a normal therapeutic evaluation, will be asked to enroll in this study. As a pilot study, we are interested in observing significant changes ($p < 0.05$) in either Ashworth Rigidity or Spasm scores related to catheter tip location along the spinal axis. Each subject will serve as their own control and will be assessed by the same rater throughout the study. The subjects will initially undergo temporary implantation of an intrathecal catheter placed under sedation or light anesthesia with fluoroscopic guidance. This will be done by the neurosurgeon with the intent of positioning the catheter initially in the mid-cervical region (C4) of the spine. The following day, after sedation / anesthetic effects are worn off, the subject will undergo a spasticity evaluation in the morning prior to ITB injection (See Tables 2 and 3 regarding Modified Ashworth and Spasm rating scores). Then a 50 microgram (μg) dose of IT baclofen will be injected into the CSF through the catheter. Samples of CSF (3cc) will be withdrawn from the IT catheter just prior to injection and at 10, 30, 60, 120, and 360 min following the ITB injection. The rater (Nurse Practitioner) will perform an Ashworth and Spasm rating exam on the subject at 2, 4, and 6 hours following the ITB injection. Each subject will be allowed to recover and observed overnight in the Clinical Research Center (CRC) at Vanderbilt University.

The following morning, each subject will be brought to the radiology department fluoroscopy room and the IT catheter withdrawn to the next lower level being studied – viz. T3, T10, or L2. Catheter position prior to- and after repositioning will be documented on digital radiograph. The subjects will then be returned to the CRC area and dosed with IT baclofen (50 micrograms IT baclofen). The same protocol for assessing spasticity (Ashworth score) and spasms (Spasm rating) will be performed that day associated with the new catheter position. In other words, a spasticity assessment will be performed just prior to injection, and at 2 hour intervals following injection up to 6 hours after injection. Likewise, a CSF sample will be withdrawn just prior to injection, and at logarithmic intervals up to 6 hours following injection. Each CSF sample will be no more than 3 cc and must represent a clean sample of CSF from the subject.

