At the end of the fifth day of study, the IT catheter will be withdrawn and a stitch placed over the hole in the skin. The subject will be allowed to stay overnight for observation and then released the following morning. Implantation of the ITB pump will be determined as usual by the implanting neurosurgeon and his staff (*note: The decision as to whether the subject or the clinical team decides to implant an ITB pump is outside the scope of this project, and would be considered part of their routine medical care following the trial of ITB*).

Selection of subjects. We will attempt to enroll ten subjects for each disease category by the end of two years. A total of 20 subjects would be enrolled to complete this study. We wish to enroll subjects with similar mechanisms of spasticity for each disease category. Our initial disease categories will involve subjects who have spasticity from very different mechanisms to determine if ITB dosing is significantly different due to origin of spasticity. One group of subjects would have spasticity due to spinal cord injury and are paraplegic, thereby recognizing that their spasticity originates from the lower half of the spinal cord in general. Another group of subjects would have spasticity due to cerebral palsy and are

quadriparetic, thereby recognizing that their spasticity originates from loss of upper motor neurons as a result of cerebral disease (typically associated with a perinatal infarct). Other disease categories, such as cervical spine SCI, stroke, hereditary spastic paraparesis, multiple sclerosis, can be considered in the future if a significant difference ($p < 0.05$ on ANOVA analysis) exists between the two broad categories represented in this pilot study.

There may be reasons why subjects may not be able to complete the study. Some foreseeable reasons include:

- Intradural blockage that prevents advancing the IT catheter to the level of C4, verified by a total MRI of the spine (Cervical, Thoracic, and Lumbar levels), without contrast injection, sagittal views only.
- Significant left over effect of the previous day's administration of IT baclofen thereby prevent a detectable change in spasticity in subsequent injections
- Allergic reaction to IT baclofen
- Withdrawal of the subject from the study
- IT catheter malfunction
- Significant headache from CSF withdrawal
- CSF leak that is intolerable (headache or otherwise) from the IT catheter entry site

Results Anticipated:

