The data will be collected according to the following schedule per patient.

Table 1. Study variables and the timing of data collection. Each table is for a specific catheter location within a given patient. This table, for example, would be filled out 4 times corresponding to the four different catheter locations studied each day.

Time	Catheter Location	Modified Ashworth Score	Spasm Score	CSF Sample
Baseline	C4, T3, T10, L2	0-4	0-4	3cc
Injection (50µg)	-	-	-	-
1 min	-	-	-	3cc
2 min	-	-	-	3cc
10 min	-	-	-	3cc
20 min	-	-	-	3cc
60 min	-	-	-	3cc
2 hours (120min)	-	0-4	0-4	-
4 hours (240 min)	-	0-4	0-4	-
6 hours (360 min)	-	0-4	0-4	-
Total				18 cc / day

Table 2. Modified Ashworth Scale for Grading Spasticity

Grade	Clinical Rating of Tone
0	No increase in tone
1	Slight increase in muscle tone, manifested by a catch and release, or by minimal resistance at the end of the range of motion when the affected

	part(s) is moved in flexion or extension
1+	Slight increase in muscle tone, manifested by a catch, followed by minimal resistance throughout the remainder (less than half) of the ROM
2	More marked increase in muscle tone through most of the ROM, but affected part(s) easily moved
3	Considerable increase in muscle tone, passive movement difficult
4	Affected part(s) rigid in flexion or extension

[figure not shown]
Table 3. Penn Spasm Frequency Scale

Spasm Score	Spasm Frequency
0	No spasms
1	Mild spasms induced by stimulation
2	Infrequent full spasms occurring less than once per hour
3	Spasms occurring more than once per hour
4	Spasms occurring more than 10 times per hour

Spasm Severity	Severity Rating
1	Mild
2	Moderate
3	Severe

For a given subject, the data will be analyzed for the following effects:

1. What was the effect of identical baclofen doses (50µg) administered at different spinal levels within each subject on rigidity? (expect reduction in score over 4-6 hours with possible return towards baseline at 6-10 hours)
2. What was the effect of identical baclofen doses (50µg) administered at different spinal levels within each subject on spasms? (expect reduction in score over 4-6 with possible return towards baseline at 6-10 hours)
3. Is there a significant difference in location of the catheter on the maximum reduction in either spasticity or spasm scores? (expect this to show as the largest “dip” in scores on 3D graph)

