4. Is there a “washout” effect from day to day? (if so, expect the baseline scores to be lower each day) If present, this would suggest that the daily dosing is too high.

[figure not shown]

For each group (SCI vs CP), the data will be analyzed as follows:

1. What catheter location caused the greatest change in spasticity scores? (the location of the catheter – C4, T3, T10 or L2 – would be noted and averaged among the ten subjects). Expect that

SCI group would favor greater change when catheter is located at T10 or L2. Expect that CP group might not show a significant difference in catheter location.

2. What catheter location caused the greatest change in spasm scores? (the location of the catheter – C4, T3, T10 or L2 – would be noted and averaged among the ten subjects) Expect that SCI group would favor greater change when the catheter is located at T10 or L2. Expect that the CP group would not have much spasm change based on catheter location.

Parameter	SCI Paraplegic (n=10)	CP Quadriparetic (n=10)
Greatest change in Ashworth Score vs Location	? ANOVA	? ANOVA
Greatest change in Spasm Rating vs Location	? ANOVA	? ANOVA
Difference in Ashworth Score between days (assess washout effect)		

Subject Recruitment and Length of Study:

We expected to be able to recruit 20 patients for this study within two years. The subjects would be solely recruited and managed through the Adult Neurosurgery practice at Vanderbilt. Patients would be approached for enrollment after first choosing to undergo an ITB trial for the treatment of their spasticity.

Procedure/Activity	Frequency
Patient consent	Clinic visit 1 1
MRI Total Spine without contrast	Outpatient Radiology 1
Implantation of intrathecal catheter under light sedation and fluoroscopy guidance to C4	Inpatient MCE Day 1 1 Transfer to CRC after wake-up from MCE procedure (CRC Day 1)
Baclofen Injection (50µg)	Inpatient CRC Day 2
Modified Ashworth Rigidity testing and Spasm rating	Inpatient CRC Day 2 at 2, 4, and 6 hours following injection
CSF Specimen 3cc	Inpatient CRC Day 2 10 min, 30 min, 60 min, 120 min, 360 min
Repositioning of intrathecal catheter to next lower level or T3 under fluoroscopy	Inpatient Radiology Day 3 1 (for this day)
Baclofen Injection (50µg)	Inpatient, CRC, Day 3
Modified Ashworth Rigidity testing and Spasm rating	Inpatient, CRC Day 3 at 2, 4, and 6 hours following injection
CSF Specimen 3cc	Inpatient CRC Day 3 10 min, 30 min, 60 min, 120 min, 360 min

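### Item 4 takes a day-to-day fall in pre-dose scores as a sign of too much daily baclofen, but scores alone cannot separate carry-over from a non-drug day trend

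*Combined protocol and SAP*

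**What the plan says.** Under Results Anticipated, the within-subject list opens with "For a given subject, the data will be analyzed for the following effects". Item 4 asks about a day-to-day washout effect, by which the plan means residual drug. The sign of it is given as "if so, expect the baseline scores to be lower each day", and the reading as "If present, this would suggest that the daily dosing is too high".

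The plan takes residual drug seriously elsewhere. Its reasons for non-completion include a lingering effect of the previous day's "administration of IT baclofen thereby prevent a detectable change in spasticity in subsequent injections". The Goal section describes the half-life of intrathecal baclofen as poorly understood. Items 1 and 2 of the same list, on the other hand, expect scores to move back towards baseline perhaps 6 to 10 hours after the dose.

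On design, Methods starts every catheter at C4 and has the "IT catheter withdrawn to the next lower level being studied" each following morning. The schedule table gives one 50 µg injection on each of Days 2, 3, 4 and 5. Each subject is their own control.

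**The concern.** Item 4 goes from lower morning scores to residual baclofen, and from there to a remark about dosing. The first step needs some contrast between mornings that follow a dose and comparable mornings that do not. The design has none: the only morning without an earlier study injection is Day 2, which is also the first assessed morning for everyone. Anything else that lowers scores over the week would produce the same pattern, and item 4 names no such alternative.

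At stake is a sentence in the pilot's report. Applied as written, the rule could produce a tentative statement about dosing from a pattern that the scores cannot attribute to drug.

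**Working it through.** The plan states no figure for carry-over, so there is none to reproduce. The question is whether the effect can be identified from the planned scores, and that needs no assumed SD or trend.

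**Inputs.** Four pre-dose scores per subject, on Days 2, 3, 4 and 5 (Methods; Table 1). Earlier study doses on those mornings: 0, 1, 2, 3 (schedule table). Same dose, interval and order in every subject (Methods). Ten subjects per group (Selection of subjects).

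**Free day effects.** Let score = subject + day effect + c × x, where x describes carry-over and is 0 on Day 2. With indicators D3, D4 and D5 for the later days:

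- Present after any previous-day dose: x = (0, 1, 1, 1) = D3 + D4 + D5.
- Any other profile common to all subjects: x = (0, a, b, e) = a·D3 + b·D4 + e·D5.

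Either way x is an exact combination of columns already in the model, so it adds no rank:

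| Data | Subject + day columns | Rank without x | Rank with x |
|---|---|---|---|
| One subject | 1 + 3 | 4 | 4 |
| Ten subjects | 10 + 3 | 13 | 13 |

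More subjects do not help, because all of them share the same x.

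**Linear trend.** Suppose the non-drug trend is a straight line, d = (0, 1, 2, 3). Carry-over that builds equally with each dose is x = (0, 1, 2, 3), the same column. Rank stays at 2 for one subject (1 + 1) and 11 for ten (10 + 1). This is the steady fall that item 4 describes. A fall of (0, −1, −2, −3) fits a trend of −1 per day with no carry-over, a carry-over of −1 per earlier dose with no trend, or any split between them.

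**Where separation is possible.** If the trend is assumed strictly linear and carry-over constant at (0, 1, 1, 1), rank rises from 2 to 3 (11 to 12 for ten subjects). The correlation of d with x is 1.5 / √(5 × 0.75) = 0.77. If instead a fraction r of each dose's effect remains the next morning, x = (0, r, r + r², r + r² + r³). The correlation with d is then 0.80 at r = 0.05, 0.96 at r = 0.5, 0.995 at r = 0.8 and exactly 1 at r = 1 (values of r assumed). For r below 1, separation comes only from the assumed curve shapes, and the documents support no particular shape.

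**The case against.** The strongest reply is that the sentence is already cautious. It only suggests, it sits among anticipated results, and it is neither a test nor a stopping rule. That stands, and it limits the weight of the point. But the caution concerns strength; only one explanation is offered.

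The second reply is that the plan already collects drug-level evidence. This also stands. The Goal section introduces the CSF samples with "In order to provide initial data regarding CSF baclofen washout, samples of spinal fluid obtained just prior to- and following IT baclofen administration", and Specific Aim 3, Methods and Table 1 all include a pre-injection sample. A reader might infer from the later phrase "sample small amounts of CSF at key anatomical sites along the spinal axis as an independent secondary study protocol" that this CSF work is set apart from the trial. That phrase closes a different sentence, about sampling at anatomical sites. What is missing is only a link from item 4 to these samples.

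Two further inferences are tempting and should not be drawn:

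- *That item 4 confuses too large a dose with too short an interval.* Daily dosing can mean the regimen, 50 µg per day. For assumed half-lives of 4, 8, 12 and 24 h, 25 µg every 24 h leaves the same residual before the fourth dose as 50 µg every 28, 31, 34 or 40 h or so. Both changes mean less drug per day. One dose and one interval cannot choose between them, but the sentence need not be read as choosing.
- *That recovery from catheter placement would imitate carry-over.* Methods says that "after sedation / anesthetic effects are worn off, the subject will undergo a spasticity evaluation in the morning prior to ITB injection". Any sedation left over could lower Day 2 tone, so recovery might raise later scores instead. The documents give no direction. A single step after Day 2 is also not the steady fall that item 4 describes.

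**Conclusion.** The point holds as a cheap improvement. Pre-dose scores alone cannot separate residual baclofen from a non-drug day trend, because day and prior dosing coincide in every subject. With free day effects this follows from the schedule and needs no assumption about variance or trend size; it assumes only that the carry-over profile is common to all subjects. With a linear trend it is exact when carry-over accumulates equally, and otherwise depends on assumed shapes.

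The documents do not show that a non-drug trend exists, how large it would be or which way it would run. The finding is that the scores could not reveal the difference, not that carry-over is absent. A reader might also infer that this undermines the main hypotheses or the dosing of subjects. It does not: H01, H02 and the doses given make no use of the sentence. The effect is confined to what may be concluded on a secondary question.

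**What to change.** Replace the dosing sentence in item 4 with:

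> A fall in pre-injection Ashworth or Spasm scores will be reported as possible carry-over or time trend. It will be taken to suggest that the daily regimen (amount or interval) is too intense only if pre-injection CSF baclofen on Days 3–5, compared with the Day 2 pre-dose sample, shows that drug remains, noting that catheter level changes with day.

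This needs no new visit, procedure or sample: Methods and Table 1 already include the pre-injection ratings and CSF. The schedule table lists only post-injection times, so it is worth confirming that the pre-injection ones are carried out.

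There are two costs. The statement has to wait for the delayed CSF assay. And each morning's sample comes from a different level, so a low or absent concentration at the new tip does not rule out drug elsewhere. CSF can show whether drug remains; it cannot by itself show that the drug caused the fall, or whether amount or interval should change.

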- H₀₁: There is no significant ($p > 0.05$) difference in clinical spasticity (as measured by using the Modified Ashworth Spasm Rating Score) when the same amount of baclofen is delivered (50 μ g) to the cervical, thoracic, or lumbar area on separate days.
- H₀₂: There is no significant ($p > 0.05$) difference in the response to Lioresal Intrathecal (baclofen injection) between patients with spinal versus cerebral origin of spasticity relative to catheter tip placement.

Specific Aims:

1. Measure the degree of spasticity based on the Modified Ashworth Scale for Grading Spasticity in patients undergoing daily, single ITB bolus injections through an intrathecal catheter located in the mid-cervical (C4), mid-thoracic (T3), thoraco-lumbar (T10) and upper lumbar (L2) regions.
2. Measure the Spasm Rating of patients undergoing daily, single ITB bolus injections through an intrathecal catheter located in the mid-cervical (C4), mid-thoracic (T3), thoraco-lumbar (T10) and upper lumbar (L2) regions.

3. Sample CSF at each of the catheter tip locations just prior to ITB injection. Sample CSF at 1, 5, 10, 20, 60 min following ITB administration.
4. Each subject will receive prophylactic antibiotics for the duration of the IT catheter placement.

Methods:

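### H₀₂ asks whether the effect of catheter location differs between SCI and CP, but no section specifies a test of that group-by-location question

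*Combined protocol and SAP*

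**What the plan says.** All references are to the combined protocol and SAP.

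- **Hypotheses, H₀₂.** The null is no difference in response "between patients with spinal versus cerebral origin of spasticity relative to catheter tip placement".
- **Goal.** The second goal is to find out "whether the origin of spasticity influences the effect of Lioresal Intrathecal (baclofen injection) on ITB catheters located in the cervical, thoracic or lumbar regions". The same section adds that "the disease origin may also have a significant impact on baclofen dosing relative to the placement of the catheter".
- **Results Anticipated, group analyses.** These open with "For each group (SCI vs CP), the data will be analyzed as follows". For each scale, the location giving the greatest change "would be noted and averaged among the ten subjects".
- **Results Anticipated, results table.** The row "Greatest change in Ashworth Score vs Location" and the matching spasm row each hold two entries, one under SCI and one under CP. Each entry is the word ANOVA preceded by a question mark. No cell compares the two columns.
- **Selection of subjects.** Other disease categories may be considered later "if a significant difference ($p < 0.05$ on ANOVA analysis) exists between the two broad categories". No outcome, factor or model term is given.
- **Outcome.** Methods is interested in change on either the Ashworth or the spasm score, and item 3 of the per-subject questions uses the maximum reduction on either scale. Nothing says which scale decides H₀₂.
- **Expected pattern.** SCI is expected to respond more at T10 or L2. For spasticity in CP: "Expect that CP group might not show a significant difference in catheter location".

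**The concern.** H₀₂ is a statement about a difference of differences: whether the profile of response over C4, T3, T10 and L2 has the same shape in SCI as in CP. An analysis within SCI and another within CP each ask whether location matters in that group. Neither compares the two profiles. Averaging each subject's best location does not compare the groups either, and, taken at face value, it averages location labels.

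The between-category ANOVA does compare the groups, but the reader cannot tell on what. If it is a group main effect, it compares response averaged over locations, which is a different question from H₀₂. If it includes the interaction, it may be the right test, but the text does not say so.

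H₀₂ is one of only two hypotheses, and a significant between-category difference is the stated condition for considering further disease groups. Without a named term, that decision could rest on a comparison that says nothing about catheter location.

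**Working it through.** **The plan's own figures.** The plan states no power, effect size, SD or within-subject correlation. The only figure to reproduce is the sample size: 2 × 10 = 20, which agrees.

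**Does any analysis contain the H₀₂ contrast?**

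| Place | What is compared | Group-by-location contrast? |
|---|---|---|
| Per-subject questions 1–4 | Locations or days within a subject | No |
| Group analyses 1–2 | Best location within one group | No |
| Results table | Locations within each group column (tentative) | None shown |
| Selection of subjects | SCI against CP, term not named | Cannot be told |

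**Why the choice of term matters.** From the document: n = 10 per group, four locations, each subject measured at all four, α = 0.05. Assumed: normal scores, independent errors with within-subject SD 1, and between-subject SD s_b of 0.5 to 2. In SCI, T10 and L2 exceed C4 and T3 by d; CP is flat. This is the pattern the plan expects.

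*Interaction test, F(3, 54).* The centred SCI profile is (−d/2, −d/2, d/2, d/2). Half of it goes to each group's interaction effect, so all eight cells are ±d/4, and λ = 10 × 8 × d²/16 = 5d².

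- d = 1.0: λ = 5.00, power 41%
- d = 1.2: λ = 7.20, power 57%
- d = 1.5: λ = 11.25, power 78%

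*Group main effect, F(1, 18).* A subject's mean over four locations has variance s_b² + 1/4. For a group difference Δ, λ = Δ² / [0.2 × (s_b² + 0.25)].

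- CP's flat level equals the SCI average: Δ = 0, rejection 5%.
- CP's flat level equals SCI's C4/T3 level, or its T10/L2 level: |Δ| = d/2 = 0.6 at d = 1.2. For s_b = 0.5, 1, 1.5 and 2, λ = 3.60, 1.44, 0.72 and 0.42, and power = 43.5%, 20.6%, 12.7% and 9.5%.

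The location pattern is the same in all these cases; only CP's overall level moves the main-effect result. A simulation of 40,000 trials at s_b = 1 and d = 1.2 gave 57% for the interaction in both settings, and 5.0% and 20.7% for the main effect.

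*The reverse error.* Let SCI and CP differ by 1.0 SD equally at every location, with no interaction. Then λ = 1 / [0.2 × (s_b² + 0.25)] = 10, 4, 2 and 1.18 over the same s_b values. The main effect is significant in 85%, 47%, 27% and 18% of trials, and the interaction in 5%.

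**What the interaction test cannot do.** The 95% CI half-width for a between-group difference, with t(54) = 2.005, is 2.005 × √(4/10) = 1.27 SD for a contrast of two locations. For T10/L2 against C4/T3 it is 2.005 × √(2/10) = 0.90 SD.

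The catheter moves down in one fixed order, so day and location coincide. With no location effect and a drift of c SD per day in one group only, λ = 10 × 5c²/2 = 25c². The interaction is then significant in 6%, 20% and 50% of trials at c = 0.1, 0.3 and 0.5.

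**The case against.** **The between-category ANOVA may already include the interaction.** Location is the natural second factor in this design, and a two-way ANOVA fits the wording as well as a one-way. This stands. A reader might infer that the plan commits to a group main effect and so tests the wrong hypothesis. The document does not support that: a test with no named term cannot be pinned to one term, and the criterion is offered as a guide to future work, not as the H₀₂ test.

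**The results table is a shell.** Its entries carry question marks and sit under a heading about anticipated results. This also stands. Even the within-group ANOVAs are tentative, so the fault is that no test of H₀₂ is specified, not that a wrong one has been fixed.

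**Discordant within-group results.** A reader might infer that significance in SCI without significance in CP would be reported as a group difference. Under the working assumptions, two groups with the same true profile would disagree in this way in up to about 50% of trials (near d = 0.8). But no section says that such a result will be read so, and that figure should not be charged to the plan.

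**It is a pilot with little power for an interaction.** True, but the plan states null hypotheses with a p-value threshold and makes further work depend on p < 0.05. Low power is a reason to report intervals, not to leave the term unnamed.

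**Conclusion.** The concern holds as a gap in specification. H₀₂ and the second goal pose a group-by-location question. The group analyses are set within SCI and within CP, the averaged best location compares nothing between groups, and the one between-group ANOVA does not say what it tests. It is more than missing detail, because the analyses that are described do not deliver a test of one of the two hypotheses.

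The size is illustrative only. For the pattern the plan expects, at d = 1.2, the interaction test has 57% power, against 5% to about 44% for a main effect, depending on CP's overall level and the between-subject SD. These figures rest on assumed effect sizes and SDs, normal scores and independent errors. Normal scores are a simplification for these ordinal scales. The figures show the direction of the problem and do not predict what this trial would find.

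**What to change.** 1. Analyse the maximum reduction from the same-day baseline at all four locations in one repeated-measures or mixed model with subject, group, location and group-by-location.
2. Provide for unequal correlation over the four days: a Greenhouse-Geisser correction, or an unstructured covariance with small-sample degrees of freedom. In a simulation with assumed serial correlation or subject-specific slopes and no true interaction, the uncorrected test rejected in 5.8% to 7.9% of trials, against 4.3% to 4.9% with Greenhouse-Geisser.
3. Test H₀₂ by the interaction, and name in advance the scale that decides it.
4. State in Selection of subjects which term the between-category criterion uses.
5. Replace the averaged best location with the mean change at each location per group, and between-group differences in location contrasts with 95% CIs.
6. State beside the result that the fixed order C4, T3, T10, L2 confounds location, and the interaction, with day and carry-over.

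The cost is analysis wording only; Table 1 already schedules the scores. The downside is modest power at 10 per group, about 41% to 78% for d = 1.0 to 1.5 under the working assumptions, so a non-significant interaction would not show equal location patterns. The model supplies the test that matches H₀₂ but does not remove the fixed-order confounding.

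### Read literally, the group rule names the best catheter level by averaging subjects' best locations, which pulls the answer towards mid-spine; the text should say that the change in score at each level is averaged

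*Combined protocol and SAP*

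**What the plan says.** The stated goal is "to determine whether there is a significant therapeutic advantage to place the ITB catheter within the cervical, thoracic or lumbar region of the spine". The levels studied are "mid-cervical (C4), mid-thoracic (T3), thoraco-lumbar (T10) and upper lumbar (L2) regions" (Specific Aims), and the planned group size is ten (Methods, Selection of subjects: "We will attempt to enroll ten subjects for each disease category by the end of two years").

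In Results Anticipated, the list of analyses for each group (SCI vs CP) opens with the question "What catheter location caused the greatest change in spasticity scores". Its answer is that "the location of the catheter – C4, T3, T10 or L2 – would be noted and averaged among the ten subjects". Item 2 repeats the same parenthetical for spasm scores: the location again "would be noted and averaged among the ten subjects".

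The expected results follow directly: "SCI group would favor greater change when catheter is located at T10 or L2", and "Expect that CP group might not show a significant difference in catheter location".

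The table beneath has one row for greatest change in Ashworth score against location and one for spasm rating. Each cell holds only a question mark and the word ANOVA. No model, location coding, contrast or rule for choosing a level is given. Nothing else in the documents says how a group's best level will be named.

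**The concern.** The object of the averaging, as the sentence is written, is the location. A location is a label, and a mean of labels estimates the centre of the subjects' best levels, not the level with the largest effect. Three consequences follow.

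- The mean can fall where no subject did best.
- Every subject contributes a best level even if the four levels do not differ. The scores are coarse (0-4), so ties are possible, and no tie rule is given.
- A subject with a large advantage at one level counts the same as a subject with a trivial one.

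The two situations that the plan itself anticipates are the ones affected. The CP group may show no location effect, and there the rule will still report a mid-spine level. The SCI group may do best at L2, and there the rule pulls the answer up towards T10.

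**Working it through.** The plan states no figure for this rule, so there is none to reproduce. The check follows the rule as written.

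**Inputs from the documents:** four levels (C4, T3, T10, L2); ten subjects per group; each subject's location of greatest change is averaged.

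**Assumptions, not in the documents:** rank coding C4=1, T3=2, T10=3, L2=4; the mean is read to the nearest level, with exact midpoints shared equally; subjects are independent. As a second coding, count vertebrae from C1: C4=4, T3=7+3=10, T10=7+10=17, L2=7+12+2=21.

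**Step 1. No location effect (each level best with probability 1/4).**
- Mean of one code: (1+2+3+4)/4 = 2.5. Variance: (1+4+9+16)/4 − 2.5² = 1.25. SD of the mean of ten: √(1.25/10) = 0.354.
- The result reads as C4 if the ten codes sum to 14 or less, and half the time if they sum to 15. Of 4¹⁰ = 1,048,576 equally likely sequences, 1+10+55+220+705 = 991 have sums of 10 to 14, and 1,902 sum to 15.
- P(C4) = (991 + 1,902/2)/1,048,576 = 0.00185, and by symmetry P(L2) is the same.
- P(T3 or T10) = 1 − 2×0.00185 = 0.996.
- Vertebral coding: expected mean (4+10+17+21)/4 = 13.0; P(T3 or T10) = 0.5885 + 0.4091 = 0.998.

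**Step 2. Subjects split between the ends (k best at C4, 10−k at L2).**
- Rank mean = [k + 4(10−k)]/10 = 4 − 0.3k. At k=5 it is 2.5, midway between T3 and T10. At k=2 it is 3.4 and at k=8 it is 1.6, both inside 1.5 to 3.5. At k=1 (3.7) and k=9 (1.3) it reads as an end level.
- Vertebral mean = [4k + 21(10−k)]/10 = 21 − 1.7k. At k=5 it is 12.5. At k=2 it is 17.6 (nearest T10) and at k=8 it is 7.4 (nearest T3).
- Under both codings, every split from 8:2 to 2:8 reads as T3 or T10, where no subject did best.

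**Step 3. A clear L2 majority (70% best at L2, 10% at each other level; assumed).**
- Rank: expected mean 0.1×(1+2+3) + 0.7×4 = 3.4, below the 3.5 boundary with L2. The exact distribution gives T10 59%, L2 41%.
- Vertebral: expected mean 0.1×(4+10+17) + 0.7×21 = 17.8, below the boundary of 19. T10 71%, L2 27%.

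**Step 4. Comparison with averaging the change at each level.** 100,000 simulated groups of ten, with independent normal changes of SD 1 (assumed); rank coding, midpoints rounded up.

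| Truth (assumed) | Largest mean change picks | Averaged location reads |
|---|---|---|
| No location effect | each level about 25% | T3 or T10, as in step 1 |
| Five best at C4, five at L2, by 1.5 SD | C4 or L2, about 98% | T3 or T10, about 99.8% |
| L2 best by 1 SD | L2, about 97% | L2 about 17%, T10 about 79% |

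**The case against.** The strongest reply is that the parenthetical is loosely worded and was meant to say that the scores at each location are averaged over the ten subjects. The surrounding text supports this. The expectations beside it compare change between levels, and the table row sets change in score against location, which suits an ANOVA with location as the factor. This may well be the intention. But the sentence does not say it, two analysts could follow it to different answers, and it needs rewording under either reading.

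A reader might infer that the rule undermines the pilot's hypothesis tests. The documents do not support that. H01 and H02 concern differences in spasticity and in response at the 0.05 level, and the decision to study other diseases later is tied to an ANOVA result. Nothing says that the averaged location feeds those tests or overrides them. Nor is the size of change lost from the whole plan: the subject-level list asks about maximum reduction by location. It is lost only in the step that names the group's best level.

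A reader might also infer that the rule makes the SCI expectation of T10 or L2 come true by chance about half the time. That is not particular to this rule. With no effect, picking the level with the largest mean change also lands on T10 or L2 about 25% + 25% = 50% of the time.

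Finally, this is a 20-subject pilot that records every score at every level, so the right summary can still be produced later. That bears on severity and is accepted.

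**Conclusion.** The point holds for the naming of each group's best level, on the literal wording of items 1 and 2. Under that wording the answer is drawn to T3 or T10 almost regardless of the truth: about 99.6% of groups with no location effect (99.8% with vertebral coding), and every C4/L2 split from 8:2 to 2:8. Even a 70% majority for L2 is more often reported as T10.

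The exact percentages depend on an assumed coding and on reading the mean to the nearest level, and step 4 also on assumed effect sizes and normal changes. The direction does not depend on the choice between the two codings tried. It would not arise if the authors intended to average the change at each location, which the text leaves open.

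This should be fixed before analysis. It is not a fault that stops the study, since all the data needed are already planned.

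**What to change.** Replace the parenthetical in items 1 and 2 with wording such as:

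> The change in score at each level (C4, T3, T10, L2) will be averaged over the group's subjects (mean, or median for ordinal scores), with within-subject differences between levels and 95% intervals. The number of subjects whose greatest change was at each level will be shown as counts, with ties shown as ties.

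Add that the level with the largest average change will be described as best only alongside those intervals, so that no optimum is claimed when the levels do not differ. Picking the largest mean does not give that protection by itself, because it still names some level when there is no effect. The counts matter too: in a 5:5 split between the ends, the largest mean favours one end or the other about equally often, and only the counts show the split.

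The cost is a few sentences in the analysis text. No new data, visits or assessments are needed.
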